If the patient decides to withdraw we will then ask the patient if we can still collect their demographic and delivery data. If they allow this, then they will be included in the analysis and this will be stated in our results once the study is written. No identifiers will be included in the results. If they would like to withdraw completely we will not collect any further data and we will not include them in our analysis.

Procedures for Investigator to Withdraw subjects:

There is no circumstance that the patient will be withdrawn without their consent. There is no anticipated reason that a patient would need to be terminated from the study.

How participants will be identified:

Every patient that requires nifedipine starts at 30 mg XL daily.

If they break through (elevated BPs above 160/110) they will get extra nifedipine 10 mg(rapid acting). When a patient is noted to require a higher dose of medication, they will be asked by their physician if they are willing to participate in the study. If the patient agrees, a member of the research team will approach the patient and discuss the study with the patient. The next day patients will be randomized to be either in the 60 mg Procardia XL Q daily group vs the 30 XL Q 12h group.

Also if BPs are persistently above 150/105 (≥ 50% of the BPs over the first 24h after the first dose), the next day their dose will be increased to 60 mg and they will also be asked to participate in the study and consent will be obtained if they are agreeable to be randomized to receive either 60 XL daily or 30 XL Q 12h.

How research will be introduced to participants:

Once patient is noted to require a higher dose of medication either because they have severe range BPs despite their first dose of Procardia XL 30 mg or persistent elevated Bps \geq 150/100 postpartum (or 160/100 for those with CHTN) the patient will be asked if

they are willing to participate in a study. This will initially be done by the physician taking care of the patient. If so, a member of the research team will be notified and then approach the patient. In a private setting, they will be introduced to the study and will be given as long as they need to decide whether they would like to participate in the study.

This is usually until the next dose is due (24h after the administration of the first dose of Procardia XL 30 mg).

How participants will be screened:

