By looking at the antepartum and the postpartum patients that had insufficient response to 30 mg of Procardia XL (defined as those patients that received 30 mg of Procardia XL and required additional rapid acting nifedipine within the next 24h to improve control of BPs or whose BPs were persistently above 150/100 or 160/100 for CHTN in the postpartum period). Primary physicians taking care of these patients will be informed of this study and once they identify patients that meet criteria and are willing to participate in the study, they will notify one of the members of the research team. We will review clinical information from their medical records and if they do in fact meet all the requirements to participate in the study the patients will be approached to discuss the study in detail and obtain their consent.

Risks to subjects:

Overall there is minimal risk to subjects who participate in the study. In terms of the medication itself, calcium channel blockers are a class of drugs considered first line treatment by the American College of Obstetricians and Gynecologists to improve elevated BPs antepartum in cases of chronic hypertension and postpartum.

Small amount have been shown to cross the placenta, however to date no known association with birth defects have been found with reassuring long term follow-up of babies up to 1.5 years. It is not associated with adverse perinatal outcomes and furthermore, nifedipine does not appear to adversely affect uterine or umbilical blood flow.

It is a safe medication, however potential side effects include peripheral edema (most common side effect, dose related, 10-30%), flushing (23-27%), headache (10-23%), dizziness (23-27%), fatigue (6%), constipation (<2%), nausea (11%), and muscle cramps (8%). These are not life threatening, but in the case a patient can't tolerate the medication, they will be changed to another antihypertensive drug.

Risks associated with blood draw from a vein are uncommon but may include momentary discomfort at the site of the blood draw, possible bruising, redness, and swelling around the site, bleeding at the site, feeling of lightheadedness when the blood is drawn and rarely infection at the site of the blood draw.

Description of Procedures Taken to Lessen the Probability or Magnitude of Risks:

No special precautions will be taken due to the fact that this medication is routinely used for control of BPs in these patients.

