Studies have also shown no alteration of fetal cardiac output of fetal heart rate.

Maternal side effects with nifedipine seldom occur and there is rarely a need to stop the drug as a result of these.

Description of the study design

This is a Pilot Study for a Randomized controlled trial comparing two groups: Patients receiving 60 mg of Procardia once daily and those receiving the same dose divided as 30 mg of Procardia XL Q 12h. This study is expected to last 24 months and during this period of time we are planning to recruit 20 patients (10 in each group). Approximately 2cc of blood will be obtained from each patient at 24h from the administration of the 60 mg of Procardia XL or the first dose of 30 mg after randomization in the group receiving twice daily dosing. This will be send to the laboratory at Mount Sinai Hospital where the levels of Procardia will be calculated.

We plan to report demographics and clinical characteristics of patients enrolled in the study. The distribution, variability, and confidence intervals of plasma levels will be reported for those randomized into the twice daily 30 mg and once daily 60 mg Procardia XL groups. Additionally, the distribution of blood pressure levels collected every 4 hours, within 24 hours after treatment, for each group will be presented descriptively. Patient reported side effects during treatment will be reported as frequencies and proportions. The intention of these preliminary data would inform the feasibility of a larger efficacy randomized controlled trial.

Description of the procedures being performed:

This is a Pilot study for a Randomized controlled trial comparing two groups: Patients receiving 60 mg of Procardia once daily and those receiving the same dose divided as 30 mg XL Q 12h.

This study will include all pregnant patients and patients up to 6 weeks postpartum who are between the ages of 18-55.

Exclusion criteria include

- All patients receiving other antihypertensive medication
- All patients with a contraindication to nifedipine: Hypersensitivity to nifedipine or other calcium − channel blocker, cardiogenic shock, concomitant administration with strong CYP34A inducers (rifampim, rifabutin, phenobarbital, phenytoin, carbamazepine, St Johns Wort) → significantly reduces nifedipine efficacy, impaired liver function → Patients with hepatic impairment (liver cirrhosis) have a longer disposition half-life and higher bioavailability of nifedipine than healthy volunteers.

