This study will be conducted on the labor floor, antepartum or postpartum floor at Mount Sinai West Hospital. When a patient's BP is persistently elevated after a dose of 30 mg of Procardia XL (requiring at least an extra dose of short acting nifedipine) the dose is increased to 60 mg Procardia XL.

Also if BPs are persistently above 150/105 (≥ 50% of the BPs over the first 24h after the first dose), the next day their dose will be increased to 60 mg and they will also be asked to participate in the study. Patients will be randomly assigned to receive 60 mg of Procardia XL either once daily or divided in 2 doses of 30 mg given 12h apart.

Depending on the group the person gets randomized into they will receive 60 mg of nifedipine at 0h vs 30 mg of nifedipine at 0h followed by 30 mg extra at 12h, These medications will be administered by a nurse or physician on the floor.

At the end of the 24h (plus or minus 30 min) a blood sample (2cc) with be obtained and sent to Mount Sinai Hospital to determine serum Procardia levels. This blood samples will be stored until this research study is finished and will be disposed after. A total of 2 cc of blood will be obtained from each patient. Also the patient will take a survey of side effects of the BP medication. BPs will be measured Q 4h and documented at 0h, 4h, 8h, 12h, 16h, 20h and 24h (plus or minus 30 min)

Description of the source records that will be used to collect data about subjects:

In order to collect data about the side effects, a member of the research team will provide a questionnaire to the patient at the end of the 24 h and all questionnaires will be placed in a locked cabinet in the PI's office in Mount Sinai West. All other data about demographics, pregnancy, as well as all BPs documented throughout the 24h period will be collected using labor and delivery electronic medical record system (Epic). Levels of medication will be obtained from the laboratory section.

Description of Data that will be collected including Long term follow up:

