The patient will be given as much time as they need to consider consenting for the study. The patient will be given as much time as they need to consider consenting for the study. Each patient that requires additional procardia during the first 24h after the initial dose of Procadia 30 mg XL is administered with be approached to participate in the study. They will be given time until administration of the second dose of Procardia is due (24h from the initial dose). At this time they will be given either 60 mg once or 30 mg followed by 30 mg at 12h.

What languages other than english will be used

Any language can be used as long as an approved interpreter is available for that language at the time of consent.

The primary investigator's primary language is spanish. This will also facility explanation of the study to the participating spanish speaking population.

Description of Health Information that will be viewed, recorded or generated:

See appendix for variables.

How PHI Will Be Protected from Improper Use or Disclosure

Primary outcome data to be collected includes: Serum Procardia level at 12h and 24h. Other information that will be recorded includes BP at 0h, 8h, 16 h and 24h and side effects such as peripheral edema (not present prior to initiation of treatment), headache, dizziness, fatigue, constipation, nausea, muscle cramps. Demographic data will also be collected such as age, race, BMI, gravity, parity. We will collect information regarding previous use of antihypertensive (before pregnancy or during pregnancy), reason for BP control (preeclampsia, CHTN, postpartum hypertension), timing of inclusion: Antepartum (gestational age), postpartum.

Description of Non-Health information that will be viewed or recorded:

Patients demographics including age, race, BMI, gravity and parity will be viewed and recorded.

Explanation why research could not be practicably conducted w/o access to and use of PHI:

In order to conduct this study we must look at the PHI in order to obtain information from the clinic, office and antepartum floor that will allow us to answer our research question.

Explanation why research could not be practicably conducted w/o a waiver or alteration of authorization:

We will be consenting patients under our care. As such, HIPPA authorization will be provided

How PI will be protected from improper use or disclosure:

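### All patients have taken nifedipine before 0h, but the plan sets no systematic 0h symptom record, so each arm's side-effect frequency can include symptoms that began earlier

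*Combined protocol and SAP*

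**What the plan says.** **Exposure before 0h.** Under How participants will be identified, "Every patient that requires nifedipine starts at 30 mg XL daily". Patients who break through also receive rapid-acting nifedipine. How participants will be screened describes one route of entry as patients who "received 30 mg of Procardia XL and required additional rapid acting nifedipine within the next 24h"; the other is persistently raised blood pressure on the first dose. Waiting period for obtaining consent places the approach to patients needing more drug "during the first 24h after the initial dose of Procadia 30 mg XL is administered". The randomised regimen begins when the next dose is due, 24h after the first.

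**Assessment.** Blood pressure has a 0h value in Description of the procedures being performed: "BPs will be measured Q 4h and documented at 0h, 4h, 8h, 12h, 16h, 20h and 24h". For side effects, Description of the source records says that "a member of the research team will provide a questionnaire to the patient at the end of the 24 h". No earlier questionnaire is described. Description of Procedures Taken to Lessen the Probability or Magnitude of Risks adds that nurses assess symptoms, that side effects are charted, and that the team takes side-effect data from the medical record.

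**Reporting.** Description of the study design and the Data Analysis Plan carry the same text. Blood pressures "within 24 hours after treatment, for each group will be presented descriptively", and then "Patient reported side effects during treatment will be reported as frequencies and proportions". The data list under How PHI Will Be Protected counts edema only if it was absent before treatment began. It puts no such limit on the other symptoms and does not say which dose begins treatment.

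**The concern.** A symptom reported at 24h may have begun on the assigned regimen, on the earlier 30 mg dose or a rapid-acting dose, or before any nifedipine. With nothing recorded systematically at 0h, a reader of the within-arm frequencies cannot separate these.

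The edema restriction shows that the protocol sees the issue for one symptom, but no planned research assessment supports it. Pre-existing edema is plausible here. Preeclampsia is a qualifying diagnosis, and the section on risks to pregnant women and fetuses cites a preeclampsia study in which edema decreased in 12 of 24 women on nifedipine. Edema that decreased was there beforehand, although that population may differ from this one.

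What is at stake is timing within each arm. Expected Direct Benefit to Subjects suggests that dividing the dose may lessen side effects, and the pilot's frequencies are meant to inform a larger trial.

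**Working it through.** **Step 1: timeline from the text.**

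- About 24h before 0h: first 30 mg XL dose. No research symptom form is described.
- Between that dose and 0h: rapid-acting nifedipine for some patients; routine ward observation.
- 0h: first randomised dose. Blood pressure is documented; no symptom form is described.
- 24h: blood pressure, blood sample and side-effect questionnaire.

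**Step 2: the reporting window.** The plan does not define treatment in the side-effect sentence. The sentence before it refers to the 24 hours after treatment for each group, so the randomised 24h is the natural reading. On that reading, symptoms that began before 0h fall outside the intended window but can still be counted.

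**Step 3: what a carried-over symptom does.** The plan has no power or precision figure to reproduce; the stated total is 2 × 10 = 20. For one arm with n = 10, let

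- b = proportion with the symptom at 0h,
- s = share of those whose symptom persists and is reported at 24h,
- e = new-onset rate among patients free of it at 0h.

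Raw 24h frequency = s·b + (1 − b)·e.

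New since 0h, over all patients = (1 − b)·e.

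Difference = s·b, whatever the value of e. If s = 0 the difference is zero. One carried-over case is 1/10 = 10 points.

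**Step 4: illustration only.** The documents give neither b nor s. I assume b from 2% to 30%. The ends are borrowed from Risks to subjects (constipation under 2%, edema up to 30%), so 2% is a ceiling for constipation. These are general rates, not rates 24h after a first 30 mg dose, and elsewhere the protocol says "Maternal side effects with nifedipine seldom occur".

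| Assumed b | Expected at 0h per arm, 10·b | Chance of at least one, 1 − (1 − b)^10 | s·b if s = 0 | s·b if s = 0.5 | s·b if s = 1 |
|---|---|---|---|---|---|
| 2% | 0.2 | 1 − 0.98^10 = 18% | 0 | 1 point | 2 points |
| 10% | 1 | 1 − 0.90^10 = 65% | 0 | 5 points | 10 points |
| 30% | 3 | 1 − 0.70^10 = 97% | 0 | 15 points | 30 points |

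The span of 0 to 30 points reflects the assumptions and is not an estimate.

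**Step 5: between arms.** Randomisation gives both arms the same expected b. If the regimens differ in how long symptoms persist, that is an effect of the regimen, not a bias. Chance imbalance remains. With X and Y independent binomial (10, b), P(|X − Y| ≥ 2) is 24%, 39% and 46% at assumed b of 10%, 20% and 30%. This is ordinary sampling error at this size, but without 0h data it could not be seen.

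**The case against.** **Charting already covers it.** These are ward patients whose nurses assess symptoms, and the team may extract side effects from the record. This stands in part: it would be wrong to infer that no 0h information will exist. But the plan fixes no time point or checklist for those notes, and the source-records section assigns side effects to the questionnaire and the other clinical data to the electronic record. The notes are a partial, unsystematic reference.

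**The questionnaire or appendix may ask about onset.** It may; neither is in the supplied text, so onset or recall wording cannot be excluded. Even so, recall at 24h is weaker than a status recorded at 0h.

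**The edema restriction may refer to the first nifedipine dose.** This is a fair reading and it stands. A 0h form alone would not then supply the reference, and tying the restriction to 0h would treat edema that arose on the first 30 mg dose as pre-existing. The sponsor has to say which is meant.

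**The plan promises only descriptive frequencies, and its main purpose is plasma levels.** Correct, and this is why the point is minor.

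**Stronger readings.** A reader might infer that the arm comparison of side effects is biased. Randomisation rules that out in expectation. A reader might also infer that the frequencies will be inflated by some stated amount. The documents give no 0h rate and no persistence rate, so they support only that earlier symptoms can be included.

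**Conclusion.** The point holds as a minor, low-cost improvement to a secondary descriptive outcome. All patients are exposed to nifedipine before 0h, and the supplied text describes no protocol-specified, systematic symptom assessment at 0h. Within-arm frequencies can therefore mix earlier symptoms with those that began on the assigned regimen, and the edema restriction cannot be applied systematically.

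The size is unknown: none if nothing persists, and 10 points in an arm for each carried-over case. The conclusion assumes that side effects during treatment means the randomised 24h, and that the unseen questionnaire and appendix do not already record onset. It does not touch the plasma-level outcome.

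**What to change.** 1. Give the same short checklist just before the first randomised dose, with a simple severity grade at both 0h and 24h. Without a grade, worsening cannot be identified.
2. Add one item at 0h asking whether edema was present before the first nifedipine dose.
3. State whether the edema restriction is measured from the first 30 mg dose or from 0h.
4. Report symptoms that are new, or worse by grade, since 0h beside the raw 24h frequencies. Use all randomised patients as the denominator and show missing forms.

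The cost is twenty extra short forms, the severity grades, and a brief contact timed to dosing, which may be separate from the consent visit. No patients or blood draws are added. Asking at 0h may prompt more reporting at 24h and so raise the raw frequencies. The form shows timing, not cause. Because carried-over symptoms that worsen would count as new or worse, s·b is the most the checklist could separate out. No gain in precision is claimed. The form is best in place before enrolment, since 0h status cannot be reliably reconstructed afterwards.

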Determine the mean plasma levels and standard deviations of Procardia at 24h after Procardia XL is administered as a 60 mg daily dose and the mean plasma levels after it is given as a 30 mg twice daily dose. This pilot study will provide us with information to design a randomized controlled trial to test the hypothesis that pregnant patients taking 60 mg once daily of Procardia XL will have lower plasma levels and insufficient BP control towards the end of 24h compared to 30 mg of Procardia XL given twice daily.

Background:

Antihypertensive therapy has been used in pregnant patients antepartum to improve blood pressure (BP) elevation in cases of chronic hypertension, and postpartum for persistent hypertension after delivery in cases of gestational hypertension and preeclampsia, as well as for management of chronic hypertension.

There is limited evidence regarding the precise BP level at which antihypertensive therapy is indicated during pregnancy for chronic hypertension. Given the limitations of data as well as higher likelihood of outpatient therapy with less frequent blood pressure monitoring, treatment has been suggested in pregnant patients when systolic BP is \geq 160 mmHg and at a lower diastolic BP threshold of 105 mm Hg [1], however some providers may initiate therapy at systolic BPs \geq 150 mmHg.

Antihypertensive therapy has not been shown to improve fetal condition or to prevent preeclampsia. However, such therapy controls acceleration of BP, reduces antepartum hospitalization due to severe hypertension and should help prevent maternal complications from uncontrolled hypertension such as cardiovascular (congestive heart failure and myocardial ischemia), renal (renal injury or failure), or cerebrovascular (ischemic or hemorrhagic stroke) damage. [1]

Drugs such as methyldopa, labetalol, and nifedipine in many occasions are used as first line agents for control of hypertension in pregnancy.

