The aim of this pilot study is to investigate the distribution of plasma levels of Procardia at 24h after Procardia XL is administered as a 60 mg daily dose and the mean plasma levels after it is given as a 30 mg twice-daily dose. So far there are no studies providing this information which is essential to design a future randomized control trial that will allow us to determine whether 60 mg daily of Procardia XL is equivalent to 30 mg twice daily or if patients on 30 mg of Procardia XL twice daily have higher plasma levels of medication and improved BP control towards the end of 24h.

Studies from the FDA have determined plasma levels of Procardia XL at different doses. Plasma levels have been reported after administration of 30 mg and 90 mg of Procardia XL, however there is no

information after 60 mg of Procardia XL is administered or after twice daily dosing is given. This information is however necessary to plan a larger scale randomized controlled trial to compare both regimens.

Secondary outcome will be effective control of BP throughout the day (4h, 8h, 12h, 16h, 20h and 24h) defined as BPs below 160/105 and frequency of side effects of nifedipine including peripheral edema (most common side effect, dose related), flushing, headache, dizziness, fatigue, constipation, nausea, and muscle cramps.

Sites: Approved. Mount Sinai West Hospital.

Funding my Mount Sinai: Yes

Number of Subjects 20 Patients in total. 10 in each group.

Specify other setting of Human Research: Antepartum, Labor and Delivery and Postpartum at Mount Sinai West Hospital

Feasibility of Meeting Recruitment Goals: Feasible. We have at least one patient per week who requires antihypertensive medication in the antepartum, postpartum, or labor and delivery floor. The primary investigator or co-investigators will by notified by the providers taking care of these patients who meet criteria and are willing to participate in the study and we will approach them to discuss any further details and obtain consent.

Facilities to be used for conducting research: We will be conducting our research on the antepartum ward, labor and delivery and postpartum ward as well as the MFM fellow office located at Mount Sinai West Hospital.

Inclusion:

Antepartum or postpartum patients between the age of 18-55 requiring 60 mg of Procardia XL to control elevated blood pressures secondary to preeclampsia, gestational hypertension, or chronic hypertension.

Exclusion:

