The purpose of this study is to investigate the mean plasma levels and standard deviations of Procardia at 24h after Procardia XL is administered as a 60 mg daily dose and the mean plasma levels after it is given as a 30 mg twice-daily dose. This will provide essential information to calculate an appropriate sample size for a future randomized control trial that will be appropriately powered to identify if different doses result in similar plasma levels or if twice daily medication achieves higher levels at 24h. We will then be able to determine if higher levels translate into improved control of BP in pregnant women and postpartum.

Provisions to Protect the Privacy Interests of Subjects:

The patients will be approached by the primary physician to determine if they are willing to participate in the study. Once they agree, the physician will notify the investigator. The patient will then be approached by a member of the study team. All research related discussions will be held in the patient's private room. Any questions will be answered and fully discussed to maximize patient comfort. Patients will be allowed time to consider participation and we will explain to patients that we will follow up their information (Bps, side effects, Procardia Levels) but will not contact them directly. We will also assure the patient all the steps that will be taken to protect their privacy.

Economic impact on subjects:

We do not see any foreseeable additional costs to subjects for participating in this research study. The patient is going to take the same dose of medication either once daily or in divided doses. Internal funding will be provided by Mount Sinai for testing of Procardia plasma Levels and the individuals will not be responsible for the cost of the blood test.

Data for Assessing Potential Risks to Pregnant Women and Fetuses:

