Protected Health Information (PHI) will be collected and used in the study. No PHI will be disclosed. Only study personnel will have access to subject information. The study investigators will collect medical information about the subject over the course of the study. Study data will be entered into a deidentified research database, using a unique code numbering system. A code number linked to subject identity will be used instead of names. The code number will not be derived from any patient identifiers, such as patient name or medical record number. The record linking the subjects' name with their assigned codes will be kept on a password protected file on a secure departmental drive. Only the PI will have access to this file. All study forms will be kept private and stored in a locked file cabinet in a secure location in the office of the PI. The computerized research database will be on a password-protected file within the OB/GYN department at Mount Sinai West. The linked code and dates of service are the only patient identifiers to be collected onto the computerized database spreadsheet along with the subject's medical information needed for the purposes of the study. Once data collection and analysis is completed, the linked code and data will be deleted.

When and How PHI Will Be Destroyed:

The files containing the data and linking files (containing PHI) will be deleted once all data has been analyzed. This will likely be approximately within 1 year of study completion.

Location Where Data Will Be Stored

The research data file is stored on a secure "departmental" network drive and the file will be password protected.

Duration Data will be stored

Data will be stored until the data is analyzed, within 1 year from study completion.

Location where date will be stored:

The research data file is stored on a secure "departmental" network drive and the file will be password protected.

Steps That Will Be Taken to Secure the Data during Storage, Use, and Transmission

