The study investigators will collect medical information about the subject over the course of the study. Study data will be entered into a de-identified research database, using a unique code numbering system. A code number linked to subject identity will be used instead of names. The code number will not be derived from any patient identifiers, such as patient name or medical record number. The record linking the subjects' name with their assigned codes will be kept on the computer in a separate secure folder. All files are password protected on a secure server.

Data Analysis Plan Including Any Statistical Procedures:

We plan to report patient demographics and clinical characteristics enrolled in the study. The distribution, variability, and confidence intervals of plasma levels will be reported for those randomized into the twice daily 30 mg and once daily 60 mg Procardia XL groups. Additionally, the distribution of blood pressure levels collected every 4 hours, within 24 hours after treatment, for each group will be presented descriptively. Patient reported side effects during treatment will be reported as frequencies and proportions. The intention of these preliminary data would inform the feasibility of a larger efficacy randomized controlled trial.

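### Should the pilot's analysis plan also commit to a between-arm estimate and a confidence interval for the SD of the 24h plasma level?

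*Combined protocol and SAP*

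**What the plan says.** The section Data Analysis Plan Including Any Statistical Procedures, repeated almost word for word under Description of the study design, sets out the whole plasma-level analysis, by regimen: "The distribution, variability, and confidence intervals of plasma levels will be reported for those randomized". Neither place mentions a difference, a ratio, an analysis scale, or an interval tied to a particular parameter.

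The Objectives ask for by-regimen summaries: "Determine the mean plasma levels and standard deviations of Procardia at 24h after Procardia XL is administered as a 60 mg daily dose", together with the corresponding levels under twice-daily dosing. The size is given as "Number of Subjects 20 Patients in total. 10 in each group", and allocation is random: "Patients will be randomly assigned to receive 60 mg of Procardia XL either once daily or divided in 2 doses".

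Under Benefits to society the protocol states what the results are for: "This will provide essential information to calculate an appropriate sample size for a future randomized control trial that will be appropriately powered" to tell whether levels are similar or are higher at 24h with twice-daily dosing. Under When and How PHI Will Be Destroyed it adds: "The files containing the data and linking files (containing PHI) will be deleted once all data has been analyzed".

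**The concern.** Patients are randomised between two regimens, and the later question is comparative, yet the plan summarises each arm separately. Two items seem to be missing: an estimate of the contrast with its confidence interval, and a statement of how uncertain the SD is.

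The second matters more, because the SD enters a sample-size formula squared. A designer who takes a point estimate from 10 or 20 patients at face value can easily underpower the next trial.

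The deletion of the data files seems to make this worse. Plasma levels may be skewed, so the later designers may want log-scale inputs. If only raw means and SDs survive, those inputs might be out of reach.

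**Working it through.** **Inputs.** There are 10 patients per arm (Number of Subjects). The documents give no SD, CV, effect size, margin, alpha or power, so the pilot's size has no calculation to reproduce and results are in units of the SD. The CVs of 30% and 60%, the lognormal model, and the 80% power and two-sided 5% level for the later trial are assumptions.

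**1. Imprecision of the SD.** Under normality the 95% limits are s × √(df/χ²), using the 97.5% and 2.5% quantiles of χ². The later N is proportional to SD².

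| Basis | df | χ² quantiles (2.5%, 97.5%) | SD multiplier | N multiplier |
|---|---|---|---|---|
| One arm | 9 | 2.70, 19.02 | 0.69 to 1.83 | 0.47 to 3.33 |
| Both arms pooled | 18 | 8.23, 31.53 | 0.76 to 1.48 | 0.57 to 2.19 |

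The N of a two-arm trial depends on the sum of the two arm variances, so with similar SDs the 18-df row is the relevant one. The multipliers depend on df alone. Once n and the SD are reported, the interval adds no new information.

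**2. Consequence for the later trial.** Suppose that trial were sized at 80% power on the unadjusted SD; the protocol does not say it will be. True power is below 70% when s/σ < (0.524 + 1.960)/2.802 = 0.887. The chance of this is P(χ² < df × 0.887²), which is 28% at 18 df and 37% at 9 df. The risk comes from how the later protocol would use the SD. Printing an interval in the pilot report does not by itself reduce it.

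**3. Precision of the contrast.** The 95% half-width is t(0.975, 18) × √(2/10) = 2.101 × 0.447 = 0.94 SD. On the log scale the SD is √ln(1 + CV²), which is 0.294 at CV 30% and 0.555 at CV 60%. The interval for a ratio is therefore about ×/÷ exp(0.94 × 0.294) = 1.32, or ×/÷ exp(0.94 × 0.555) = 1.68. This is too wide to supply an effect size.

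**4. What can be rebuilt from n, mean and SD?** The raw difference and its interval follow exactly. For the log scale, 200,000 lognormal samples of 10 per arm were simulated. The log-SD was rebuilt as √ln(1 + (SD/mean)²), and the log geometric mean as ln(mean) minus half the square of that.

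| Quantity | CV 30% | CV 60% |
|---|---|---|
| Rebuilt ÷ direct geometric mean ratio, central 95% | 0.98 to 1.02 | 0.93 to 1.08 |
| Standard error of log ratio, rebuilt vs direct | 0.131 vs 0.131 | 0.250 vs 0.248 |
| Rebuilt ÷ direct log-SD, one arm, central 95% | 0.84 to 1.14 | 0.72 to 1.20 |
| Relative RMSE of log-SD against the true value, rebuilt vs direct | 0.239 vs 0.234 | 0.243 vs 0.234 |

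The third row looks worrying because it compares two noisy estimates with each other. The fourth compares each with the truth: nearly all the error is sampling error, which direct reporting would not remove. A modest loss remains at CV 60%, where the pooled rebuilt log-SD is biased by about −8% (direct: about −1%) and the resulting N has a median of 0.87 times the one based on the direct log-SD.

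**The case for a change.** The strongest case for a change is that the plan leaves out the precision of the very quantity the pilot exists to supply, and that adding it costs a few lines and no patients, visits or samples. The phrase about confidence intervals names no parameter; its natural reading is an interval for each arm's mean, and even a generous reading yields no contrast. Log-scale results cannot be rebuilt exactly from raw summaries, and the files will be deleted.

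Part of this stands. The wording is loose, no contrast is promised, and the log-SD bias at a high CV is real.

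The rest is weaker than it looks. Any statistician sizing the next trial can apply the multipliers above. The plan also promises the distribution of levels, which with 10 patients per arm may well show quantiles or individual values, though it does not commit to that. The Objectives say the pilot informs the study team's own design of the next trial, and deletion comes only after analysis is complete. Nothing suggests that the people who need the sizing inputs would lose the data first. The log scale is itself a preference that rests on an assumed distribution; the documents state none.

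**Conclusion.** No change to the plan is needed. The objective is the mean and SD under each regimen, the planned summaries deliver it, and the comparison is deferred to a later trial. For a 20-patient pilot that is a fair choice, and the absence of a hypothesis test is not a fault.

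The uncertainty in the SD is genuine: about 0.57 to 2.19 times in N for a two-arm trial with similar arm SDs, assuming normality and all 20 patients analysed. It comes from the pilot's size, and the wording of its report would not alter it.

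Analysts can add the difference or ratio, labelled as estimation only, and the SD with its interval when they write up. The one quantity that direct reporting would improve is the log-SD when variability is high, by roughly seven percentage points of bias at an assumed CV of 60%. That is small beside the sampling error.
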